8.1.1 Analysis Populations

All participants who have received least 1 dose of study medication will be included in the safety analysis (safety population). The efficacy analysis will be performed on an "intention-to-treat (ITT)" basis and a "PP" basis (see definitions below). Participants with major protocol violations will be excluded from the latter. For this purpose, protocol violations that could interfere with the objectives of the study, incorrect concomitant medications or violation of the inclusion/exclusion criteria etc. will be assessed as 'minor' or 'major' in collaboration with the Sponsor. The criteria for this assessment will be defined before analysis. Listings will be prepared to show the eligibility of all participants. These listings will be presented in a Data Review Meeting.

Definition of Analysis Populations:

Population	Description
Screening	All participants who signed the ICF
population	
Safety	All participants who received any dose of the IMP
population	
Intention-to-	All participants included in the safety population for whom the primary
treat (ITT)	endpoint is evaluable
analysis set	•
Per protocol	All participants included in the ITT analysis set who complete the
(PP) analysis set	study without major protocol violation

The primary analysis will be performed on the PP analysis set. In addition, a sensitivity analysis will be performed using the ITT analysis set. All efficacy assessments on the PP analysis set will be repeated for the ITT analysis set.

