8.1.10 Interim Analysis

After completion of Stage 1, i.e. after all participants have completed the visit at Day 28 and their T concentration levels are available, an analysis of the primary efficacy parameter will be performed analysing the number and proportion of participants reaching castration level by Day 28 with the loading dose of teverelix TFA.

The study will proceed during the analysis and all other efficacy, safety and demographic parameters will be evaluated at the end of the study (full analysis, Stage 2).

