Data will be captured using the eCRF provided by the designated CRO. The eCRF is specifically designed to meet the data recording requirements of the clinical study protocol. Only the investigator and his/her authorised staff who are trained appropriately on the eCRF system are allowed to fill in the eCRFs or to make corrections, and will have access to the data or may change data (however this access will be granted without the possibility to delete the original entries). After completion, each eCRF will be electronically signed and dated by the investigator. Central laboratory test results will be imported automatically into the eCRF. The overall procedures for quality assurance of clinical study data are described in the respective standard operating procedures (SOPs) of the CRO. A document describing the functional specification will be prepared by the CRO in cooperation with the eCRF provider and will be approved by the Sponsor prior to the start of the study. This functional specification will describe in detail the structure and functionality of the eCRF. In addition, the CRO will prepare a data management plan to describe the procedures and processes of data collection and data coding.

Electronic validation of the data entered in the eCRFs will take place (e.g. check of ranges, consistency, and plausibility). All plausibility checks will be defined in the data validation plan to be approved by the Sponsor. Additionally, the eCRFs will be reviewed by qualified data management and medically qualified personnel for completeness, consistency, and plausibility. Any data anomalies will be communicated to the site(s) for clarification/resolution (data query). Procedures of data entry and correction will be tracked and appropriately documented in the audit trail of the eCRF.

9.2 **Documentation**

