### **3.7 Per Protocol (PP) Analysis Set**

All participants included in the ITT analysis set who complete the study without major protocol violation will be included in the PP analysis set. Participants with major protocol violations will be excluded.

Protocol Violations will be classified as either 'major' or 'minor' in collaboration with the Sponsor. The criteria for this assessment will be defined before database lock. Patient inclusion or exclusion from this population will be confirmed following data review and prior to database lock. Listings will be prepared to show the eligibility of all participants prior to database lock. These listings will be presented in a Data Review Meeting.

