## 6.8 Efficacy Analyses

The efficacy endpoints will include collected and derived, continuous and categorical variables. Continuous variables will be summarised as detailed in Section 5.1.2.

The primary analysis will be performed on the per-protocol (PP) population. In addition, a sensitivity analysis will be prepared in the intention-to-treat (ITT) population. All efficacy assessments on the PP population will be repeated for the ITT population.

The primary analysis is carried out on the PP population as there is no comparator and therefore no risk of bias towards one group. Also, due to the study design, it is not expected that there will be many protocol violations. Furthermore, it is not preferable for subjects who fail to attend the Day 28 visit to get their test to be included as non-responders in the primary response rate. If the response rate is below 90% in the ITT population but above in the PP, this will be considered in the interpretation of the results.

The following SAS code chooses the exact/Clopper-Pearson CI for the proportion of responders with two possible ways of extracting the data.

```
ods output binomialcls=<data out1>;
proc freq data=<data in> order= formatted; /* choose the correct order
option to specify which is the responder. See SAS documentation for
further details if required */
  table <responder variable> / bin(cl=exact);
  output out=<data out2>(keep=_bin_ xl_bin xu_bin) bin ;
run;
ods output close;
```

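### Membership of the primary per-protocol set can be settled after Day 28 testosterone is known, and study completion is a condition of entry, so exclusions can depend on the outcome of a single-arm rate

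*SAP*

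**What the plan says.** **Primary set.** SAP 6.8: "The primary analysis will be performed on the per-protocol (PP) population". SAP 3.7 defines it: "All participants included in the ITT analysis set who complete the study without major protocol violation will be included in the PP analysis set". The ITT set (SAP 3.4) is every dosed man with a central T result at Day 28, and all efficacy analyses are repeated on it as sensitivity analyses.

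**When membership is settled.** SAP 3.7 has violations graded as major or minor together with the sponsor. Of the grading criteria it says: "The criteria for this assessment will be defined before database lock". Of each man's status: "Patient inclusion or exclusion from this population will be confirmed following data review and prior to database lock". Protocol 8.1.1 says of the same criteria: "The criteria for this assessment will be defined before analysis". It does not say which analysis.

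**When the outcome is known.** Protocol 8.1.10 plans an analysis of the Day 28 castration rate once all Day 28 visits are done and T levels are available. It continues: "The study will proceed during the analysis and all other efficacy, safety and demographic parameters will be evaluated at the end of the study". The trial is open-label (Protocol 5.7). Protocol 9.1 adds: "Central laboratory test results will be imported automatically into the eCRF".

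**Why PP is primary.** SAP 6.8: "The primary analysis is carried out on the PP population as there is no comparator and therefore no risk of bias towards one group". The same section foresees a rate below 90% in ITT and above it in PP, and says only that this would be weighed in interpretation.

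**Withdrawal.** Protocol 4.3 makes withdrawal mandatory for lack of efficacy, with T above 2 ng/mL as its example.

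**The concern.** A per-protocol set protects an estimate only if membership is decided without knowledge of the outcome. Here the latest permitted date for that decision falls after the primary rate may already have been tabulated, and nothing states that those grading violations must not see T. The completion requirement adds a second route from outcome to membership that involves no judgement at all.

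The reasoning in SAP 6.8 does not meet this. The absence of a comparator removes bias between arms. It does not protect a single proportion read against a fixed target (90%, Protocol 8.1.2) and a fixed null (74.5%, Protocol 8.1.12). Each non-responder removed shrinks the denominator and leaves the numerator unchanged.

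At stake is the credibility of the figure that, under Protocol 8.1.12, is to support dose selection for Phase 3.

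**Working it through.** **Inputs.** Null 74.5%, alternative 90%, two-sided 5%, 50 evaluable, 80% power, 16% dropout, 60 enrolled (Protocol 8.1.12, Group 2). Clopper-Pearson intervals (SAP 6.8.1). Any hypothesis test rests on confidence intervals (SAP 5.2).

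**1. The plan's own figures.**
- Sample size: n = [(1.96·√(0.745·0.255) + 0.8416·√(0.9·0.1)) / (0.9 − 0.745)]² = 50.98. At n = 50 the normal-approximation power is 79.0%, against the stated 80%.
- Dropout: 50/(1 − 0.16) = 59.5, so 60.
- Intervals: 54/60 gives 79.5 to 96.2; 45/50 gives 78.2 to 96.7; 57/60 gives 86.1 to 99.0; 95% of 50 (47.5) gives 84.8 to 99.2. All agree with the stated intervals.

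**2. Order of events.**

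| Step | Earliest or latest time | Source |
|---|---|---|
| Day 28 rate analysed | once all Day 28 T levels are available | Protocol 8.1.10 |
| Study completion known | Day 168 or later | Protocol 3.1; SAP 3.7 |
| Violation criteria and PP status final | any time up to database lock | SAP 3.7 |

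Because PP needs completion, final membership cannot be known at the 8.1.10 analysis.

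**3. Effect of exclusions.** The documents give no number of exclusions. The scenarios assume that only non-responders are removed, so the rate goes from x/n to x/(n − k).

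| Start | Rate (95% CI) | k | After | Rate (95% CI) |
|---|---|---|---|---|
| 44/50 | 88.0% (75.7 to 95.5) | 2 | 44/48 | 91.7% (80.0 to 97.7) |
| 52/60 | 86.7% (75.4 to 94.1) | 3 | 52/57 | 91.2% (80.7 to 97.1) |
| 43/50 | 86.0% (73.3 to 94.2) | 1 | 43/49 | 87.8% (75.2 to 95.4) |

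The first two rows cross the 90% target, but their lower limits were above 74.5% before any exclusion. The third crosses 74.5% but stays below 90%.

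**4. Error rate against 74.5%, n = 50.** With no exclusions the lower limit clears 74.5% from 44 responders, and P(X ≥ 44 | 0.745) = 0.016. If up to one non-responder can be removed, 43 suffice (43/49): 0.038. If up to two, 42 suffice (42/48, lower limit 74.8%): 0.079. The nominal one-sided level is 0.025.

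**5. Completion condition.** A man withdrawn for T above 2 ng/mL does not complete, so SAP 3.7 removes him without any grading. If he was non-castrate at Day 28, this raises the Day 28 rate. If he was castrate at Day 28 and escaped later, it removes a responder and lowers it. The net direction is not known in advance.

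**The case against.** Confirming PP membership at a data review before lock is usual practice, and SAP 3.7 sets a latest date, not a required one. SAP 4.3.3 already lists deviations that lead to exclusion, including prohibited medication and visits outside the window. Protocol 8.1 requires the SAP to be signed before any study-specific analysis, so that list should predate the Day 28 analysis. Central T is batch-shipped every 3 months, which delays knowledge of it. SAP 6.8 also gives two further reasons for PP: few violations are expected, and non-attenders should not count as failures. Above all, every result is repeated on ITT, violations are tabulated and all data are listed.

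Much of this stands. The 4.3.3 list narrows the discretion, but it does not define a major violation and does not say which visits the window rule covers. Batch shipping delays knowledge of T without preventing it. The ITT repeat would show the net effect of exclusions, so a reader who inferred that a PP rate above 90% could not be told apart from selective exclusion would go too far. But ITT has no stated decision role.

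Three other stronger readings are not supported. Nothing shows that men were, or will be, excluded because of their T. Nothing shows that the SAP deliberately moved the protocol's deadline: Protocol 8.1.1 is ambiguous, and SAP 7.1 lists no such change. Nor is a PP estimate above 90% a formal success rule, since the primary analysis is descriptive.

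**Conclusion.** The point holds as a weakness in safeguards. The plan permits the criteria and membership of the primary set to be settled with Day 28 T known and analysed, states no masking, and makes membership depend on a completion condition that is itself tied to T. The justification in SAP 6.8 does not answer this.

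The possible size is one to three men: two or three exclusions can carry the estimate over 90%, and one can carry the lower limit over 74.5%. This rests on the worst-case assumption that every excluded man is a non-responder. Exclusions unrelated to T would not produce a systematic shift.

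**What to change.** - In SAP 3.7, with Protocol 8.1.1 changed to match, settle the list of major violations before the 8.1.10 analysis. This also reconciles the two deadlines.
- Define a Day 28-specific PP status that does not depend on completing the study after Day 28. Without this an early freeze cannot work.
- Classify from listings that omit post-dose T, LH, FSH and PSA, and any withdrawal for high T. Sign and date the frozen list. Report later changes without altering the primary set.
- If Day 28 results have already been seen, present the ITT rate beside the PP rate with equal prominence.
- Replace the no-comparator justification in SAP 6.8.

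**Cost.** A short wording change to both documents and an earlier, masked review meeting; no extra patients or procedures. The price is that a violation found after the freeze no longer changes the primary set.

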### **3.8 Analysis of Subgroups**

No subgroup analyses are planned.

## **4. Study Measures**

This section describes the measures that were collected and/or derived during the study at the time points specified in the Schedule of Assessments (**Error! Reference source not found.**). This includes efficacy, safety, tolerability and subject characteristics data.

The Baseline value for all variables is defined as the last non-missing measurement collected/derived prior to the first study medication administration at Visit 2/Day 0. This includes unscheduled visits.

The change from Baseline value at each post-baseline visit for all variables will be calculated as the difference between the measurement obtained/derived at the specific post-baseline visit, and the Baseline value.

The two dose groups will be analysed separately – the combined results will not be of interest for the analyses. The combined results would not be of interest as Group 2 would only open to recruitment if Group 1 was deemed ineffectual.

### **4.1 Efficacy Measures**

The efficacy endpoints described in this section will form part of the efficacy analyses and will be analysed according to the analysis methods described in Section 6.8.

#### **4.1.1 Primary Efficacy Measure**

The primary efficacy measure is the proportion of subjects achieving castration with central lab serum T <0.5 ng/mL or 1.73 nmol/L at Day 28. The denominator is the number of subjects who have a non-missing central lab T record at Day 28 in the relevant population.

---

Document:

C:\ProgramData\activePDF\Temp\DocConverter\API\Input\\$651f4dc0b253\$FE3041C5883446E892B20AB6D3F0E1BD.docx

Author: [name]

Version and Date: Version 1.0, 21 Apr 2023

Page 29 of 66

The primary parameter analysis will be performed on the PP analysis set. In addition, a sensitivity analysis will be performed on the ITT analysis set.

#### 4.1.2 Secondary Efficacy Measures

Secondary efficacy analyses include the evaluation of the following variables:

- T (Total)
- LH
- FSH
- PSA

All these variables will be assessed at the timepoints shown in Table 7 below.

**Table 7 Timepoints of Efficacy Variables**

Stage	Group	Timepoint	Variables				
			Local T	Central T	LH	FSH	PSA
Stage 1	1 and 2	Baseline (pre-dose)		○	○	○	○
		24 hours post-dose		○	○	○	
		48 hours post-dose		○	○	○	
		72 hours post-dose		○	○	○	
		Day 4		○	○	○	
		Day 7		○	○	○	○
		Day 14		○	○	○	○
		Day 21 a	○	○	○	○	○
Stage 2	1 and 2	Day 28		○	○	○	○
		Day 35	○	○	○	○	○
		Day 42		○	○	○	○
		Day 77	○				
		Day 84		○	○	○	○
		Day 119	○				
		Day 126		○	○	○	○
		Day 161	○				
		Day 168		○	○	○	○
Stage 3	2 only	Day 203	○	○	○	○	○
		Day 210	○	○	○	○	○
		Day 217	○	○	○	○	○
		Day 224 b	○	○	○	○	○
		Day 231 b	○	○	○	○	○

Document:

C:\ProgramData\activePDF\Temp\DocConverter\API\Input\\$651f4dc0b253\$FE3041C5883446E892B20AB6D3F0E1BD.docx

Author: [name]

Version and Date: Version 1.0, 21 Apr 2023

Page 30 of 66

Stage	Group	Timepoint	Variables				
			Local T	Central T	LH	FSH	PSA
		Day 238 b	○	○	○	○	○
		Day 245 b	○	○	○	○	○
		Day 252	○	○	○	○	○
		Follow up visit	○	○	○	○	○

FSH=follicle stimulating hormone; LH=luteinising hormone; PSA=prostate-specific antigen; T=testosterone

a If PSA is <0.06 ng/mL, hs PSA will be measured and reported. If PSA is ≥0.06 ng/mL then hs PSA will not be measured and reported.b These visits will only be done if local lab T result at previous visit was <1 ng/mL. If it is >1 ng/mL then their next study visit would be the Final Assessment/Follow up visit

## List of Secondary Analysis Endpoints to be Included in the Study Results:

1. Proportion of participants achieving castration level with serum T <0.2 ng/mL at Day 28.  
Percentage of participants who have T concentrations <0.2 ng/mL at the end of Stage 1 (Day 28).
2. Proportion of participants achieving castration level with serum T <0.5 ng/mL at Day 42.
3. Proportion of participants achieving castration level with serum T <0.2 ng/mL at Day 42.
4. Proportion of participants achieving castration level with serum T <0.5 ng/mL across treatment period from Day 28 until Day 168  
Note: Defined as the observed percentage of participants who have T concentrations <0.5 ng/mL (1.73 nmol/L) at all scheduled visits.
5. Proportion of participants achieving profound castration level(<0.2 ng/mL) across treatment period from Day 28 until Day 168.
6. Time to T levels falling below castration level (<0.5 ng/mL [1.73 nmol/L]) for the first time.
7. Time to (first) overstep of T castration level after achieving castration.  
Note: Overstep of T castration level is defined as the first instance of T levels being above castration level after a patient has achieved castration.
8. Time for serum T levels to be > 0.5 ng/mL after final, Day 168 injection.
9. Proportion of participants achieving castration level for LH (LH <1.1 U/L) at Day 28
10. Proportion of participants with effective LH castration level across treatment period from Day 28 until Day 168
11. Time to LH levels falling below castration level (LH <1.1 U/L) for the first time
12. Time to (first) overstep of LH castration level after achieving castration.
13. Changes from baseline in PD and PK parameters over time
14. Confirmed PSA Response Rate
15. PSA response rate at day 28
16. Number of participants with a PSA response of ≥50% reduction at the Day 168 visit
17. Number of participants with PSA response of ≥80% reduction at the Day 168 visit
18. Percent change from baseline in serum PSA concentration at each visit
19. Serum PSA concentration at each visit
20. PSA levels at each visit
21. Mean nadir PSA up to Day 168
22. Time to nadir PSA level
23. Percent change from baseline in Serum LH concentration at each visit
24. Serum LH concentration at each visit

Document:

C:\ProgramData\activePDF\Temp\DocConverter\API\Input\\$651f4dc0b253\$FE3041C5883446E8  
92B20AB6D3F0E1BD.docx

Author: [name]

Version and Date: Version 1.0, 21 Apr 2023

Page 31 of 66

25. LH levels at each visit
26. Serum T concentration at each visit
27. Percent change from baseline in Serum FSH concentration at each visit
28. Serum FSH concentration at each visit
29. FSH levels at each visit

All PK parameters analysis will be described with details in a separate SAP.

#### **4.1.2.1 Local Lab T Level**

Local lab serum T level (ng/mL) and number of subjects with local lab serum T <2 ng/mL will be measured at Screening, Visit 11/Day 21 and 7 days prior to each dosing visit. For comparison, the number of subjects with local lab serum T  $\geq$ 2 ng/mL will also be recorded. See Table 8 below.

Local laboratory data will not be reported.

**Table 8 PD Blood Sampling Schedulea**

	Day 0 (pre-dose)	24h	48h	72h	Day 4	Day 7	Day 10	Day 12	Day 14	Day 21 b	Day 28	Day 35 c	Thereafter 7 days prior to each dosing visit	Thereafter at each dosing visit and follow up visits d
T (local)														
T (central)	O	O	O	O	O	O	O	O	O	O	O	O	O	O
LH	O	O	O	O	O	O	O	O	O	O	O	O	O	O
FSH	O	O	O	O	O	O	O	O	O	O	O	O	O	O
PSA	O				O				O	O	O	O	O	O

FSH=follicle stimulating hormone; hs=high-sensitivity; LH=luteinising hormone; PD=pharmacodynamic; PK=pharmacokinetic; PSA=prostate-specific antigen;

T=testosterone

a PD blood draws should be done at the same time of day as PK blood draws (pre-dose on Day 0)b If PSA is <0.06 ng/mL hs PSA will be measured and reported. If PSA is ≥0.06 ng/mL then hs PSA will not be measured and reported.c Group 1 onlyd Including Day 203 to Final Assessment Visit for Group 2 subjects who enter Stage 3.

#### **4.1.3      Supplementary FDA Recommended Efficacy Measure**

Supplementary analysis will be conducted utilizing the Kaplan-Meier technique to estimate the proportion of patients who achieve and maintain castrate T levels (<0.5 ng/mL or 1.73 nmol/L) from Day 28 through the end of the treatment period.

### **4.2      Safety Measures**

The safety endpoints described in this section will be analysed according to the analysis methods described in Section 6.9.

#### **4.2.1      Exposure to Study Medication**

Duration of exposure, number of injections received, whether subjects received all planned injections and total dose received will be presented.

#### **4.2.2      Adverse Events**

An adverse event (AE) is any untoward medical occurrence in a participant or clinical investigation participant who is administered a pharmaceutical product. This untoward medical occurrence does not necessarily have a causal relationship with the administered treatment. An AE can, therefore, be defined as any unfavourable and unintended sign (including abnormal laboratory findings), symptom, or disease that is temporally associated with the use of a medicinal (investigational) product, whether related to that medicinal (investigational) product.

AE data will be collected from the time that informed consent was given, for the duration of the trial.

Missing AE data will be handled according to the rules specified in Section 6.9.2.

#### **4.2.3      Adverse Event Definitions**

For each AE, the investigator will document the following:

- **Signs and symptoms** of the event (if a specific disease can be diagnosed, this disease should be the reported AE; if only signs and symptoms can be evaluated, each sign or symptom should be reported as a separate AE)
- **Onset date and time** (if a change from pre-dose in a laboratory test is reported as an AE, the start date is the date of collection of the first laboratory sample that shows the change)
- **End date and time** (if a change from pre-dose in a laboratory test is reported as an AE, the end date is the date of collection of the first laboratory sample that shows a return to pre-dose level)
- **Measure taken** (none, drug treatment required, hospitalisation or prolonged hospitalisation, study discontinuation, other measures [specification])
- **Outcome** (recovered/resolved, recovering/resolving, recovered/resolved with sequelae, not recovered/not resolved, fatal, unknown)

In addition, each AE will be rated by the investigator according to the following categories:

- **Relationship to study medication:** Related, Probable, Possible, Unlikely, Not related. Investigator record from the eCRF will be reported.
- **Intensity:** Grade 1(mild), Grade 2 (moderate), Grade 3 (severe), Grade 4 (life-threatening), Grade 5 (death). This is based on National Cancer Institute (NCI) Common Terminology Criteria for Adverse Events (CTCAE), and investigator record from the electronic Case Report Form (eCRF) will be reported.
- **Seriousness:** Serious AEs reported from the time of informed consent until 31 days after the dose of study medication will be recorded on the eCRF.

Document:

C:\ProgramData\activePDF\Temp\DocConverter\API\Input\\$651f4dc0b253\$FE3041C5883446E892B20AB6D3F0E1BD.docx

Author: [name]

Version and Date: Version 1.0, 21 Apr 2023

Page 34 of 66

- **Expectedness:** Expected, Unexpected.

A treatment-emergent AE (TEAE) is defined as any new or worsening pre-existing AE with a date equal to or later than the date of IMP administration.

A treatment-emergent serious AE (TESAE) is defined as any new or worsening pre-existing SAE with a date equal to or later than the date of IMP administration.

An AE is an adverse drug reaction (ADR) if a causal relationship between a medicinal product and an AE is at least a reasonable possibility. An AE will be classified as related to study medication if the relationship to study medication was recorded (on the 'Study Adverse Events' CRF page,) as 'Unlikely', 'Possible', 'Probable', 'Related'. An AE will be classified as unrelated to study medication if the relationship to study medication was recorded as 'Unrelated'.

Any AE that leads to discontinuation of treatment will have 'Action Taken with Study Treatment' reported as 'Drug Withdrawn' on the 'Adverse Event' page.

